16.3. Appendix 3: Assessment Windows

16.3.1. Definitions of Assessment Windows for Analyses

Unless otherwise noted, laboratory data, vital signs, ECGs, Health Outcomes assessments, and genotypic/phenotypic data will be assigned to assessment windows according to actual dates rather than the nominal visit labels as recorded on the eCRF or in the laboratory database.

In most cases the window around an assessment will include all dates from the midpoints between the target day and that of the previous and the proceeding visits. The target Study Day or target Injection Study Day for is defined in Section [16.3.2](#).

For parameters which are not scheduled to be assessed at a particular visit, the all-inclusive assessment windows will still be used; however, data summaries will only report scheduled visits. Assessments at unscheduled visits will be included for “any time” and “on-treatment” time points and in data listings, as well any algorithms that make use of additional data (e.g., snapshot).

Maintenance phase assessments are assigned based on the Maintenance Phase Study Day, respectively. Extension phase assessments are assigned based on the Maintenance Phase Study day for subjects continuing CAB LA + RPV LA dosing (Q2M) into the Extension Phase, and based on the Extension Phase Study Day for subjects switching from the BIK arm to CAB LA + RPV LA dosing (Switch Q2M) for the Extension phase. Long-term Follow-up phase assessments are assigned based on the LTFU study day. See Section [16.6.1](#) for derivation of Maintenance, Extension and LTFU Study Day.

16.3.2. Definitions of Assessment Windows for Data Other than Health Outcomes

16.3.2.1. Assessment Windows for Screening, Maintenance and Extension Phase Data – Q2M OLI Subjects

All Parameters except for where noted ^(d)	Analysis Window	Target Study Day	Target Injection Study Day	Analysis Timepoint 1	Analysis Timepoint 2	Notes
	Study Day \leq 1	Study day of the earliest record		Screening	Screening	Screening
	Last available recorded value up to and including the date of first Maintenance Phase dose of IP	1		Maintenance Baseline (Day 1)	Maintenance Baseline (Day 1)	Maintenance Baseline (Day 1)
Post-dose ECG	Value taken post-dose	1		Day 1 (Post Dose)	Day 1(Post Dose)	Day 1(Post Dose)
	Injection Study Day \leq 15 and Study Day \geq 2 For those with OLI only: $2 \leq$ Study Day \leq Study Day of Last Oral Dose + 1	31	1	Month 1	Month 1	Injection 1
Urinalysis	Injection Study Day \leq 42 and Study Day \geq 2 For those with OLI only: $2 \leq$ Study Day \leq Study Day of Last Oral Dose + 1					
Post-dose ECG	Value taken post-dose Month 1					
	$16 \leq$ Injection Study Day \leq 60	61	31	Month 2	Month 2	Injection 2
	$61 \leq$ Injection Study Day \leq 120	121	91	Month 4	Month 3/4	Injection 3
	$121 \leq$ Injection Study Day \leq 180	181	151	Month 6	Month 5/6	Injection 4
Urinalysis ^(d) , CD8, CD4/CD8 ratio, fasting glucose and lipids ^(d) , weight, height, BMI, Waist and Hip Circumference, Vital Signs ^(d) , Insulin, HbA1c, HOMA-IR,	$121 \leq$ Injection Study Day \leq 192					

All Parameters except for where noted ^(a)	Analysis Window	Target Study Day	Target Injection Study Day	Analysis Timepoint 1	Analysis Timepoint 2	Notes
Renal, Bone and CCI						
	$181 \leq \text{Injection Study Day} \leq 240$	241	211	Month 8	Month 7/8	Injection 5
	$241 \leq \text{Injection Study Day} \leq 300$	301	271	Month 10	Month 9/10	Injection 6
	$301 \leq \text{Injection Study Day} \leq 360$					
Urinalysis ^(a) , CD8, CD4/CD8 ratio, fasting glucose and lipids ^(a) , weight, height, BMI, Waist and Hip Circumference, Vital Signs, CCI, Insulin, HbA1c, Renal, Bone and CCI ^(a)	$301 \leq \text{Injection Study Day} \leq 372$	361	331	Month 12	Month 11/12	Injection 7
	$361 \leq \text{Injection Study Day} \leq 420$ For those who did not continue to Extension after completing Maintenance Phase: $361 \leq \text{Injection Study Day} \leq \text{Injection Study Day of: max}(\text{Last Injection Date} + 67, \text{Date of Last Oral Dose} + 1)$	421	391	Month 14	Month 13/14	Injection 8
	$(30^*m - 59) \leq \text{Injection Study Day} \leq (30^*m)$	$30^*m + 1$	$30^*m - 29$	Month 16, 18, etc.	Month m-1/m	Injection (m/2+1)
If subject permanently discontinued study treatment:						
	Subject received at least 1 injection of IP: Date > min(LTFU ART start date, max(Last Injection Date + 67, Date of Last Oral Dose + 1)) Subject received oral CAB/RPV only: Date > (Date of Last oral CAB/RPV Dose + 1)			Follow-up	Follow-up	Follow-up

NOTES:

- Analysis windows are applied after data has been assigned to the Maintenance Phase and Extension Phase as defined in Section 16.4.1
- Study day and injection study day is defined in Section 16.6.1
- Follow-up will be derived only for participants who permanently discontinued study treatment.
- Last oral dose may be CAB/RPV or SOC ART Oral Bridging where CAB/RPV is not available due to COVID-19 impact.
- Target Injection Study Day is only applicable to Q2M OLI subjects

[a] **Urinalysis:** All parameters provided by the central laboratory under the category of urinalysis.

[b] **Lipids:** Cholesterol, HDL Cholesterol Direct, LDL Cholesterol Calculation, LDL Cholesterol Direct, Total Cholesterol/HDL Cholesterol Ratio, Triglycerides

[c] **Bone Markers:** Bone-specific alkaline phosphatase, Procollagen type 1 N-propeptide, Type 1 collagen cross-linked C-telopeptide, Osteocalcin, 25 hydroxy-Vitamin D; **Renal Markers:** Cystatin C, Retinol Binding Protein, Beta-2-Microglobulin; **CCI**

[d] Analysis windows for parameters with sparse collection are noted.

16.3.2.2. Assessment Windows for Screening, Maintenance and Extension Phase Data – Q2M D2I Subjects

All Parameters except for where noted ^(c)	Analysis Window	Target Study Day	Analysis Timepoint 1	Analysis Timepoint 2	Notes
	Study Day ≤ 1	Study day of the earliest record	Screening	Screening	Screening
	Last available recorded value up to and including the date of first Maintenance Phase dose of IP	1	Maintenance Baseline (Day 1)	Maintenance Baseline (Day 1)	Injection 1
post-dose ECG	Value taken post-dose	1	Day 1 (Post Dose)	Day 1(Post Dose)	Injection 1
Urinalysis	$2 \leq \text{Study Day} \leq 60$	31	Month 1	Month 1	Injection 2
	$2 \leq \text{Study Day} \leq 72$				
	$61 \leq \text{Study Day} \leq 120$				
	$121 \leq \text{Study Day} \leq 180$	91	Month 3	Month 3/4	Injection 3
Urinalysis ^(a) , CD8, CD4/CD8 ratio, fasting glucose and lipids ^(b) , weight, height, BMI, Waist and Hip Circumference, Vital Signs, CCI , Insulin, HbA1c, Renal, Bone and CCI	$121 \leq \text{Study Day} \leq 192$				
	$181 \leq \text{Study Day} \leq 240$	211	Month 7	Month 7/8	Injection 5
	$241 \leq \text{Study Day} \leq 300$	271	Month 9	Month 9/10	Injection 6
	$301 \leq \text{Study Day} \leq 360$	331	Month 11	Month 11/12	Injection 7
Urinalysis ^(a) , CD8, CD4/CD8 ratio, fasting glucose and lipids ^(b) , weight, height, BMI, Waist and Hip Circumference, Vital Signs, CCI , Insulin, HbA1c, Renal, Bone and CCI	$301 \leq \text{Study Day} \leq 372$				

All Parameters except for where noted ^[d]	Analysis Window	Target Study Day	Analysis Timepoint 1	Analysis Timepoint 2	Notes
	$361 \leq \text{Study Day} \leq 420$ For those who did not continue to Extension after completing Maintenance Phase: $361 \leq \text{Study Day} \leq \max(\text{Last Injection Date} + 67, \text{Date of Last Oral Dose} + 1)$	391	Month 13	Month 13/14	Injection 8
	$(30*m - 29) \leq \text{Study Day} \leq (30*m + 30)$	$30*m + 1$	Month 15, 17, etc.	Month m/m+1	Injection ((m+3)/2)
If subject permanently discontinued study treatment:					
	Date > min(LTFU ART start date, max(Last Injection Date + 67, Date of Last Oral Dose + 1))		Follow-up	Follow-up	Follow-up

NOTES:
 
 • Analysis windows are applied after data has been assigned to the Maintenance Phase and Extension Phase as defined in Section 16.4.1 • Study day is defined in Section 16.6.1 • Follow-up will be derived only for participants who permanently discontinued study treatment. • Last oral dose may be CAB/RPV or SOC ART Oral Bridging where CAB/RPV is not available due to COVID-19 impact. 
[a] Urinalysis: All parameters provided by the central laboratory under the category of urinalysis. [b] Lipids: Cholesterol, HDL Cholesterol Direct, LDL Cholesterol Calculation, LDL Cholesterol Direct, Total Cholesterol/HDL Cholesterol Ratio, Triglycerides [c] Bone Markers: Bone-specific alkaline phosphatase, Procollagen type 1 N-propeptide, Type 1 collagen cross-linked C-telopeptide, Osteocalcin, 25 hydroxy-Vitamin D; Renal Markers: Cystatin C, Retinol Binding Protein, Beta-2-Microglobulin; CCI [d] Analysis windows for parameters with sparse collection are noted.
					

16.3.2.3. Assessment Windows for Screening and Maintenance Phase Data –BIK

All Parameters except for where noted ^[a]	Analysis Window	Target Study Day	Analysis Timepoint 1	Analysis Timepoint 2	Notes
	Study Day ≤ 1	Study day of the earliest record	Screening	Screening	
	Last available recorded value up to and including the date of first Maintenance Phase dose of IP	1	Maintenance Baseline (Day 1)	Maintenance Baseline (Day 1)	
post-dose ECG	Value taken post-dose	1	Day 1 (Post Dose)	Day 1(Post Dose)	
	2 ≤ Study Day ≤ 84	57	Month 2	Month 2	
	85 ≤ Study Day ≤ 140	113	Month 4	Month 3/4	
	141 ≤ Study Day ≤ 196				
Urinalysis ^[a] , CD8, CD4/CD8 ratio, fasting glucose and lipids ^[a] , weight, height, BMI, Waist and Hip Circumference, Vital Signs, CCI, Insulin, HbA1c, Renal, Bone and CCI	141 ≤ Study Day ≤ 210	169	Month 6	Month 5/6	
	197 ≤ Study Day ≤ 252	225	Month 8	Month 7/8	
	253 ≤ Study Day ≤ 308	281	Month 10	Month 9/10	
	309 ≤ Study Day ≤ 350				
Urinalysis ^[a] , CD8, CD4/CD8 ratio, fasting glucose and lipids ^[a] , weight, height, BMI, Waist and Hip Circumference, Vital Signs, CCI, Insulin, HbA1c, Renal, Bone and CCI ^[a]	309 ≤ Study Day ≤ 378	337	Month 12	Month 11/12	
	351 ≤ Study Day ≤ Study Day of Last Maintenance BIK Dose +1	365	Month 13	Month 13/14	
If subject permanently discontinued study treatment:					
	Date> (Date of Last BIK Dose +1)		Follow-up	Follow-up	
NOTES:					

 Analysis windows are applied after data has been assigned to the Maintenance Phase as defined in Section 16.4.1 					

- Note for the BIK arm, the “every two months” are implemented as “every 56 days”, therefore the analysis windows are adjusted according to the actual visit schedules instead of nominal.
- Study day is defined in Section 16.6.1
- Follow-up will be derived only for participants who permanently discontinued study treatment.

[a] **Urinalysis:** All parameters provided by the central laboratory under the category of urinalysis.

[b] **Lipids:** Cholesterol, HDL Cholesterol Direct, LDL Cholesterol Calculation, LDL Cholesterol Direct, Total Cholesterol/HDL Cholesterol Ratio, Triglycerides

[c] **Bone Markers:** Bone-specific alkaline phosphatase, Procollagen type 1 N-propeptide, Type 1 collagen cross-linked C-telopeptide, Osteocalcin, 25 hydroxy-Vitamin D; **Renal Markers:** Cystatin C, Retinol Binding Protein, Beta-2-Microglobulin; **CCI**

[d] Analysis windows for parameters with sparse collection are noted.

16.3.2.4. Assessment Windows for Extension Phase Data – BIK subjects Switching to CAB LA + RPV LA (Switch Q2M) and choose OLI (Switch OLI)

All Parameters except for where noted ^[c]	Analysis Window	Target Extension Study Day	Target Extension Injection Study Day	Analysis Timepoint 1	Analysis Timepoint 2	Notes
	Last available recorded value up to and including the date of first Extension Phase dose of CAB/RPV	1		Extension Baseline (Month 13)	Extension Baseline (Month 13)	
	Extension Injection Study Day ≤ 15 and Extension Study day ≥ 2 For those with Ext OLI only: $2 \leq$ Extension Study Day \leq Extension Study Day of Last Extension Oral Dose +1	31	1	Month 14	Month 14	Extension Injection 1
Urinalysis ^[a] , fasting glucose and lipids ^[b]	Extension Injection Study Day ≤ 42 and Extension Study day ≥ 2 For those with Ext OLI only: $2 \leq$ Extension Study Day \leq Extension Study Day of Last Extension Oral Dose +1					
	$16 \leq$ Extension Injection Study Day ≤ 60	61	31	Month 15	Month 15	Extension Injection 2
	$61 \leq$ Extension Injection Study Day ≤ 120	121	91	Month 17	Month 16/17	Extension Injection 3
	$121 \leq$ Extension Injection Study Day ≤ 180	181	151	Month 19	Month 18/19	Extension Injection 4
	$(30*(m-14) - 29) \leq$ Extension Injection Study Day $\leq (30*(m -14)+ 30)$	$30*(m-13) + 1$	$30*(m-14) + 1$	Month 21, 23, etc.	Month m-1/m	Extension Injection (m-11)/2
If subject permanently discontinued study treatment:						
	Subject received at least 1 injection of IP: Date > min(LTFU ART start date, max(Last Injection Date + 67, Date of Last Oral Dose + 1)) Subject received oral CAB/RPV only: Date > (Date of Last oral Dose +1)			Follow-up	Follow-up	

NOTES:

- Analysis windows are applied after data has been assigned to the Extension Phase as defined in Section 16.4.1
- Extension Study day and Extension Injection Study Day is defined in Section 16.6.1
- Follow-up will be derived only for participants who permanently discontinued study treatment.
- Last oral dose may be CAB/RPV or SOC ART Oral Bridging where CAB/RPV is not available due to COVID-19 impact.
- Target Extension Injection Study Day is only applicable to Switch Q2M subjects who choose OLI during the Extension Phase

[a] **Urinalysis:** All parameters provided by the central laboratory under the category of urinalysis.

[b] **Lipids:** Cholesterol, HDL Cholesterol Direct, LDL Cholesterol Calculation, LDL Cholesterol Direct, Total Cholesterol/HDL Cholesterol Ratio, Triglycerides

[c] Analysis windows for parameters with sparse collection are noted.

16.3.2.5. Assessment Windows for Extension Phase Data –BIK subjects Switching to CAB LA + RPV LA (Switch Q2M) and choose D2I (Switch D2I)

All Parameters except for where noted ^[c]	Analysis Window	Target Extension Study Day	Analysis Timepoint 1	Analysis Timepoint 2	Notes
	Last available recorded value up to and including the date of first Extension Phase dose of CAB/RPV	1	Extension Baseline (Month 13)	Extension Baseline (Month 13)	Extension Injection 1
	$2 \leq \text{Study Day} \leq 60$	31	Month 14	Month 14	Extension Injection 2
Urinalysis ^[a] , fasting glucose and lipids ^[b]	$2 \leq \text{Study Day} \leq 72$				
	$61 \leq \text{Study Day} \leq 120$	91	Month 16	Month 16/17	Extension Injection 3
	$121 \leq \text{Study Day} \leq 180$	151	Month 18	Month 18/19	Extension Injection 4
	$(30*(m-13) - 29) \leq \text{Study Day} \leq (30*(m -13)+30)$	$30*(m-13) + 1$	Month 20, 22, etc.	Month m/m+1	Extension Injection (m-10)/2
If subject permanently discontinued study treatment:					
	Date > min(LTFU ART start date, max>Last Injection Date + 67, Date of Last Oral Dose + 1))		Follow-up	Follow-up	

NOTES:
 
 • Analysis windows are applied after data has been assigned to the Extension Phase as defined in Section 16.4.1 • Extension Study day is defined in Section 16.6.1 • Follow-up will be derived only for participants who permanently discontinued study treatment. • Last oral dose may be CAB/RPV or SOC ART Oral Bridging where CAB/RPV is not available due to COVID-19 impact. 
[a] Urinalysis: All parameters provided by the central laboratory under the category of urinalysis. [b] Lipids: Cholesterol, HDL Cholesterol Direct, LDL Cholesterol Calculation, LDL Cholesterol Direct, Total Cholesterol/HDL Cholesterol Ratio, Triglycerides [c] Analysis windows for parameters with sparse collection are noted.
					

16.3.2.6. Assessment Windows for Summary of Snapshot Data - Data assigned to Maintenance Phase Only

Snapshot Analysis Windows (If no on-treatment viral load data in default window, use expanded window)		Analysis Timepoint 1	Analysis Timepoint 2
Default^[a]	Expanded +6 Week Upper Window		
Last available recorded value up to and including the date of first Maintenance Phase dose of IP	Last available recorded value up to and including the date of first Maintenance Phase dose of IP	Maintenance Baseline (Day 1)	Maintenance Baseline (Day 1)
CAB LA + RPV LA (OLI)			
Injection Study Day ≤ 15 and Study Day ≥ 2 For those with OLI only: $2 \leq \text{Study Day} \leq 45$	Injection Study Day ≤ 42 and Study Day ≥ 2 For those with OLI only: $2 \leq \text{Study Day} \leq \text{Study Day of Last Oral Dose} + 1$	Month 1	Month 1
$16 \leq \text{Injection Study Day} \leq 60$	$16 \leq \text{Injection Study Day} \leq 72$	Month 2	Month 2
$61 \leq \text{Injection Study Day} \leq 120$	$61 \leq \text{Injection Study Day} \leq 132$	Month 4	Month 3/4
$109 \leq \text{Injection Study Day} \leq 192$	$109 \leq \text{Injection Study Day} \leq 192$	Month 6	Month 5/6
$181 \leq \text{Injection Study Day} \leq 240$	$181 \leq \text{Injection Study Day} \leq 252$	Month 8	Month 7/8
$241 \leq \text{Injection Study Day} \leq 300$	$241 \leq \text{Injection Study Day} \leq 312$	Month 10	Month 9/10
$289 \leq \text{Injection Study Day} \leq 372$	$289 \leq \text{Injection Study Day} \leq 372$	Month 12	Month 11/12
CAB LA + RPV LA (D2I)			
$2 \leq \text{Study Day} \leq 60$	$2 \leq \text{Study Day} \leq 72$	Month 1	Month 1
$61 \leq \text{Study Day} \leq 120$	$61 \leq \text{Study Day} \leq 132$	Month 3	Month 3/4
$109 \leq \text{Study Day} \leq 192$	$109 \leq \text{Study Day} \leq 192$	Month 5	Month 5/6
$181 \leq \text{Study Day} \leq 240$	$181 \leq \text{Study Day} \leq 252$	Month 7	Month 7/8
$241 \leq \text{Study Day} \leq 300$	$241 \leq \text{Study Day} \leq 312$	Month 9	Month 9/10
$289 \leq \text{Study Day} \leq 372$	$289 \leq \text{Study Day} \leq 372$	Month 11	Month 11/12
BIK Arm			
$2 \leq \text{Study Day} \leq 84$	$2 \leq \text{Study Day} \leq 98$	Month 2	Month 2
$85 \leq \text{Study Day} \leq 140$	$85 \leq \text{Study Day} \leq 154$	Month 4	Month 3/4
$127 \leq \text{Study Day} \leq 210$	$127 \leq \text{Study Day} \leq 210$	Month 6	Month 5/6
$197 \leq \text{Study Day} \leq 252$	$197 \leq \text{Study Day} \leq 266$	Month 8	Month 7/8
$253 \leq \text{Study Day} \leq 308$	$253 \leq \text{Study Day} \leq 322$	Month 10	Month 9/10
$295 \leq \text{Study Day} \leq 378$	$295 \leq \text{Study Day} \leq 378$	Month 12	Month 11/12
NOTES:			
○ Apply Snapshot analysis windows only to viral load data that is on-treatment within the Maintenance Phase (See Section 16.4.2).			

- An on-treatment viral load assessment may be assigned to more than one snapshot analysis window.
 - a. ± 6 Week window is always used at key analysis timepoints (Month 5/6 and Month 11/12). For other analysis timepoints, if no viral load data in default window, expand upper bound to +6 weeks.

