2.2. Study Objective(s) and Estimand(s) / Endpoint(s)

Objectives	Estimands/Endpoints
Primary	
To demonstrate the non-inferior antiviral activity of CAB LA + RPV LA every two months compared to a BIK single tablet regimen administered once daily over 12 months in suppressed HIV-1 infected antiretroviral therapy (ART)-experienced participants	Proportion of participants with plasma HIV-RNA greater than or equal to 50 copies/mL as per Food and Drug Administration (FDA) Snapshot algorithm at Month 12 (OLI and BIK)/Month 11 (D2I) (Intent-to-Treat Exposed [ITT-E] population)
Secondary	
To demonstrate the antiviral and immunologic response with the use of CAB LA + RPV LA every 2 months compared to a BIK single tablet regimen administered once daily	
Proportion of participants with plasma HIV-1 RNA <50 c/mL (c/mL) at Month 6 and Month 12 (OLI and BIK)/Month 5 and Month 11 (D2I) using the FDA Snapshot algorithm (Intent-to-Treat Exposed [ITT-E] population)
 
Proportion of participants with protocol-defined confirmed virologic failure (CVF) through Month 6 and Month 12 (OLI and BIK)/Month 5 and Month 11 (D2I).
 
Proportion of participants with HIV-RNA greater than or equal to 50 c/mL as per FDA Snapshot algorithm at Month 6, and Month 12 (OLI and BIK)/Month 5 and Month 11 (D2I)
 
Absolute values and changes from Baseline in viral load and CD4+ cell count over time including Month 6 and Month 12 (OLI and BIK)/Month 5 and Month 11 (D2I)

To assess viral resistance in participants experiencing protocol-defined confirmed virologic failure	Incidence of treatment emergent genotypic and phenotypic resistance to CAB, RPV, BIC, FTC, and TAF through Month 6 and Month 12 (OLI and BIK)/Month 5 and Month 11 (D2I).
To evaluate renal (in urine and blood) and bone (in blood) biomarkers in participants treated with CAB LA + RPV LA compared to BIK	Change from Baseline (Day 1) in renal and bone biomarkers at Months 6 and 12 (OLI and BIK)/Month 5 and Month 11 (D2I).
To evaluate Metabolic Syndrome for participants treated with CAB + RPV and BIK	Change from Baseline in proportions of participants with Metabolic syndrome at Months 6 and 12 (OLI and BIK)/Month 5 and Month 11 (D2I)

Objectives	Estimands/Endpoints
To evaluate insulin resistance in participants treated with CAB LA + RPV LA compared to BIK	Change from Baseline (Day 1) in homeostasis model of assessment-insulin resistance (HOMA-IR) at Months 6 and 12 (OLI and BIK)/Month 5 and Month 11 (D2I).

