CCI									
CCI									
History of Cosmetic procedures ⁹⁹								X	X

Time and Events Table for BIK to Oral Lead In – Extension Phase:

Procedure	Extension Phase				Withdrawal Assessments ^y	Long-Term Follow-up ^z
	Month					
	13	14	15	Q2M After Month 15		
Eligibility Verification (Inclusion/ Exclusion Criteria)	X ^d					
Symptom Directed Physical Exam and Medical Assessment ^f	X	X	X	X	X	X
Weight, Height and BMIs					X	
Waist Circumference					X	
Hip Circumference					X	
Vital Signs (BP, HR, Temperature) ^h					X	
12-lead ECG ⁱ					X	
HIV Associated Conditions	X	X	X	X	X	X
AEs, SAEs, Concomitant Medications	X	X	X	X	X	X
ISR Assessment for IM injection		X	X	X	X	X
Clinical chemistry and Hematology	X	X	X	X	X	X
Pregnancy Testing ^l	S	U	U	U	S	U
HIV-1 RNA and sample for storage (S) ^m	X	X	X	X	X	X
CD4+ cell count		X	X	X	X	X
CD8+ cell count					X	
Urinalysis ⁿ		X			X	
Fasting Labs Glucose, Cholesterol (Total, HDL and LDL) and Triglycerides ^o		X			X	
Whole Blood (Virology)					X	
CCI						
PBMCs ^q					X	

Procedure	Extension Phase				Withdrawal Assessments ^y	Long-Term Follow-up ^z
	Month					
	13	14	15	Q2M After Month 15		
PK sampling ^u (S)=Storage only		S	S		X	S
Oral CAB and Oral RPV Dispensation ^v	X					
IP accountability (Pill Counts)	X	X				
IM treatment administration ^w		X	X	X		
CCI						

Time and Events Table for BIK to Direct to Injection – Extension Phase:

Procedure	Extension Phase			Withdrawal Assessments ^y	Long-Term Follow-up ^z
	Month				
	13	14	Q2M After Month 14		
Eligibility Verification (Inclusion/ Exclusion Criteria)	X ^d				
Symptom Directed Physical Exam and Medical Assessment ^f	X	X	X	X	X
Weight, Height and BMI ^g				X	
Waist Circumference				X	
Hip Circumference				X	
Vital Signs (BP, HR, Temperature) ^h				X	
12-lead ECG ⁱ				X	
HIV Associated Conditions	X	X	X	X	X
AEs, SAEs, Concomitant Medications	X	X	X	X	X
ISR Assessment for IM injection	X	X	X	X	X
Clinical chemistry and Hematology	X	X	X	X	X
Pregnancy Testing ^j	S	U	U	S	U
HIV-1 RNA and sample for storage (S) ^m	X	X	X	X	X
CD4+ cell count		X	X	X	X
CD8+ cell count				X	
Urinalysis ⁿ		X		X	
Fasting Labs Glucose, Cholesterol (Total, HDL and LDL) and Triglycerides ^o		X		X	
Whole Blood (Virology)				X	
CCI					
PBMCs ^q				X	

Procedure	Extension Phase			Withdrawal Assessments ^y	Long-Term Follow-up ^z
	Month				
	13	14	Q2M After Month 14		
PK sampling ^u (S)=Storage only		S		X	S
IP accountability (Pill Counts)	X				
IM treatment administration ^w	X	X	X		
CCI					

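### The BIK Month 12 CD4+ window closes at Day 350 to make room for a Month 13 sample that CD4+ does not have, so very late BIK values drop out of the by-visit CD4+ summary

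*SAP*

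**What the plan says.** Section 16.3.2.3 sets the BIK windows by actual study day. For Month 12 (target Day 337) the default is "309 ≤ Study Day ≤ 350". A second Month 12 row, "309 ≤ Study Day ≤ 378", covers a list of exceptions that includes "CD8, CD4/CD8 ratio, fasting glucose and lipids" but does not name CD4+ count. The section's footnote explains such rows: "Analysis windows for parameters with sparse collection are noted". Month 13 (target Day 365) follows at "351 ≤ Study Day ≤ Study Day of Last Maintenance BIK Dose +1".

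In Appendix 2 (section 16.2), BIK participants have CD4+ at every Maintenance visit up to Month 12. In the oral lead-in switch schedule and in the "Time and Events Table for BIK to Direct to Injection – Extension Phase", the CD4+ cell at Month 13 is blank and the first entry is at Month 14. HIV-1 RNA and chemistry do have a Month 13 entry in both.

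Section 16.3.1 says that where a parameter is not scheduled at a visit the window still applies, but "data summaries will only report scheduled visits". Section 16.5.2 repeats this for each parameter with reference to the Time and Events table.

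Section 2.2 lists as a secondary endpoint "Absolute values and changes from Baseline in viral load and CD4+ cell count over time including Month 6 and Month 12".

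**The concern.** The Day 350 cut makes sense for a parameter sampled again around Day 365, because it shares the days between two real visits. CD4+ in BIK has no sample there, so the cut hands Days 351 onward to a visit at which CD4+ is never planned. A Month 12 CD4+ count drawn in that period loses its Month 12 label and gains no other reportable one.

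At stake is the completeness of the BIK Month 12 CD4+ summary. A valid on-treatment value for a named secondary endpoint is left out by the window rule alone, and the rule is tighter on the late side in BIK than in Q2M.

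**Working it through.** **Reproducing the plan's bound.** Section 16.3.1 places window limits at midpoints between neighbouring targets. With the BIK targets of Day 281 (Month 10), 337 (Month 12) and 365 (Month 13):

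- lower bound: (281 + 337)/2 = 309
- upper bound: (337 + 365)/2 − 1 = 350

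This gives 309 to 350 exactly. The same rule reproduces the BIK windows for Months 4 to 10, so Day 350 follows the stated rule with Month 13 as neighbour.

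**Days allowed around target for the Month 12/11 CD4+ count** (sections 16.3.2.1 to 16.3.2.3; OLI counted in Injection Study Days):

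| Group | Window | Target | Before target | After target |
|---|---|---|---|---|
| BIK | 309–350 | 337 | 337 − 309 = 28 | 350 − 337 = 13 |
| Q2M OLI | 301–360 | 331 | 331 − 301 = 30 | 360 − 331 = 29 |
| Q2M D2I | 301–360 | 331 | 331 − 301 = 30 | 360 − 331 = 29 |

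The arms are nearly equal before target and differ by 29 − 13 = 16 days after it.

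**The listed exceptions at the same visit.** For CD8 and CD4/CD8 the late side is 378 − 337 = 41 days in BIK and 372 − 331 = 41 days in Q2M. The BIK Month 12 Snapshot window (section 16.3.2.6) also ends at Day 378.

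**Where a late value goes.**

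- BIK, Day 351 onward: labelled Month 13, where neither switch schedule plans CD4+. Sections 16.3.1 and 16.5.2 then keep it out of the visit summary.
- Q2M, Day 361 onward: labelled Month 14 (OLI) or Month 13 (D2I), where the Q2M schedules do plan CD4+, so it can still be summarised.

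**Who is affected.** Appendix 2 allows ±3 days around a BIK visit, so an on-time Month 12 visit falls no later than Day 340. The first affected day is 351, which is 14 days after target and 351 − 340 = 11 days beyond the visit allowance. The SAP gives no figure for how often this happens. For scale only: about 654/3 = 218 participants are planned for BIK. If 1% to 5% of them attended that late (an assumption), 2 to 11 CD4+ values would be affected.

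**Candidate bounds.** Matching the Q2M late side gives 337 + 29 = Day 366. Matching the BIK CD8, CD4/CD8 and Snapshot windows gives Day 378, or 41 days after target.

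**The case against.** The strongest reply is that the SAP is following its own rules. Day 350 is the correct midpoint, and the wider rows are reserved for sparsely collected parameters. CD8 is drawn only at Day 1, Month 6 and Month 12 in BIK, while CD4+ is drawn at every Maintenance visit, and CD4+ is left out of the wider rows in Q2M too. All of that stands. A reader might infer that Day 350 is a slip, or that CD8 was extended because it lacks a Month 13 sample; the SAP supports neither. What the reply leaves open is that frequent sampling up to Month 12 does not supply a sample at Month 13, which is what the bound relies on.

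Three further stronger readings also fail:

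- **Late values are removed in one arm only.** Q2M values after Day 360 also leave Month 11/12. The arms differ in the allowance and in whether the next visit is a planned CD4+ visit.
- **The mismatch between the CD4+ and CD4/CD8 windows is a BIK defect.** In Q2M the limits are 360 and 372. At Month 6 they are 196 and 210 in BIK, and the Month 6/5 limits are 180 and 192 in Q2M. It is a general feature of the plan.
- **The data are lost.** The value remains for listings, and for a participant who switches it may serve as the Extension baseline. It might even appear under the pooled Month 13/14 label if the table were programmed that way, although sections 16.3.1 and 16.5.2 point against this.

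**Conclusion.** The point holds as a limited fault in one window. As written, a BIK Month 12 CD4+ count drawn 14 or more days after target has no planned visit to be reported under and is omitted from the by-visit CD4+ summary (Table 2.32), while Q2M has 29 days and a scheduled CD4+ visit to follow.

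The consequence is modest. Only very late visits are touched, and their number is unknown and probably small. Section 7.2.2 plans descriptive statistics only for CD4+, so no test or margin depends on it. The primary and key secondary endpoints use the separate Snapshot windows and are unaffected.

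The conclusion assumes that the summary is programmed as sections 16.3.1 and 16.5.2 direct, and that CD4+ is not among the blacked-out entries in the exception list. The latter is unlikely, since CD4+ is shown openly elsewhere in the SAP.

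**What to change.** In section 16.3.2.3, add a Month 12 row for CD4+ count starting at Day 309 with its own upper bound, and state which of two aims it serves:

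- **Day 366** gives BIK the same 29 days after target that Q2M has for CD4+.
- **Day 378** aligns CD4+ with the BIK CD8, CD4/CD8 and Snapshot windows. Its small downside is 41 days after target in BIK against 29 in Q2M, so the imbalance changes direction (41 − 29 = 12 days) instead of disappearing.

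Either way, start the Month 13 row for CD4+ on the following day. Keep the restriction to data already assigned to the Maintenance Phase, so that no count taken after the first Extension dose date can enter, and keep the closest-to-target rule of section 16.3.5 for multiple values. The cost is one table entry and the matching line in the derivation program. No scheduled BIK CD4+ sample at Month 13 competes for these days.
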